7.7. Changes From Protocol-Specified Safety Analyses

There are no deviations from the protocol-specified safety analyses.

8. PHARMACOKINETIC (PK) ANALYSES

8.1. PK Sample Collection

Sparse (single) PK samples will be collected at Weeks 4, 12, 24, 48 and EOT visit for PK analysis of SEL and metabolite(s), as applicable. Date and time of last dose of study drug prior to PK sample collection as well as date and time of PK sample collection will be recorded. Additionally, whether the previous dose of study drug was taken fed or fasted will be recorded.

Sparse (single) PK samples will not be collected for subjects who permanently discontinue study drug and remain on study.

A single PK blood sample will be collected at any time during each On-Treatment Visit for all subjects.

CCI

Concentrations of SEL and GS-607509 in plasma will be determined using validated bioanalytical assays. A population PK model will be developed to characterize the PK of SEL and its metabolite (as applicable). Data from this study (single PK CCI) will be combined with data from other studies in a meta-population analysis using nonlinear mixed-effects modeling techniques. Details of the population PK analysis will be provided in a separate population PK analysis report.

CCI

8.2. PK Analyses Related to Intensive PK Sampling

CCI

Concentrations of SEL and its metabolite GS-607509 in plasma will be determined using validated bioanalytical assays.

8.2.1. Estimation of PK Parameters

PK parameters will be estimated using Phoenix WinNonlin® software using standard noncompartmental methods. The linear up/log down rule will be used in conjunction with the appropriate noncompartmental model, with input values for dose level, dosing time, plasma concentration, and corresponding real-time values, based on drug dosing times whenever possible.

All predose sample times before time-zero will be converted to 0.

For area under the curve (AUC), samples BLQ of the bioanalytical assays occurring prior to the achievement of the first quantifiable concentration will be assigned a concentration value of 0 to prevent overestimation of the initial AUC. Samples that are BLQ at all other time points will be treated as missing data in WinNonlin. The nominal time point for a key event or dosing interval (τ) may be used to permit direct calculation of AUC over specific time intervals. The appropriateness of this approach will be assessed by the PK scientist on a profile-by-profile basis.

Pharmacokinetic parameters such as AUC_{τ} , λ_z and $t_{1/2}$ are dependent on an accurate estimation of the terminal elimination phase of drug. The appropriateness of calculating these parameters will be evaluated upon inspection of PK data on a profile-by-profile basis by the PK scientist.

CCI

CCI

CCI

CCI
[Redacted text block containing multiple paragraphs and bulleted points]

10. SOFTWARE

SAS® Software Version 9.2. SAS Institute Inc., Cary, NC, USA.

East 6 Version 6.5. Copyright © Cytel Inc., 1994-2018

11. SAP REVISION

Revision Date (DD MMM YYYY)	Section	Summary of Revision	Reason for Revision
3 DEC 2021			Original Version 1.0

12. APPENDICES

- Appendix 1. Schedule of Assessments
- Appendix 2. Adjustment of On-Treatment $eGFR_{cr}$ Values
- Appendix 3. Prohibited Medications That May Impact SEL Treatment Efficacy or Decrease SEL Drug Level
- Appendix 4. Data Collection of COVID-19 Data

Appendix 1. Schedule of Assessments

Study Procedures Table – Screening to Randomization

	Period	Screening	Enrollment	Run-In		Randomization	
	Visit		A	B ^a	C ^b	1 ^b	
	Visit Window (days)	30 day screening period		7 – 14 days after visit A	21 – 28 days after visit B	7 – 14 days after visit C	
Clinical Assessments	Written Informed Consent	X					
	Medical History & Demographics	X					
	Complete Physical Examination ^c	X					
	Vital Signs including Weight ^d	X	X	X	X	X	
	Height	X					
	Waist Circumference	X					
	12 Lead ECG	X					
	CCI						
	Adverse Events	X	X	X	X	X	X
	Concomitant Medications	X	X	X	X	X	X
	Study Drug Dispensing		X	X	X	X	X
	Study Drug Dosing		X	X	X	X	X
	Study Drug Bottle Return			X	X	X	X

	Period	Screening	Enrollment	Run-In		Randomization
	Visit		A	B ^a	C ^b	1 ^b
	Visit Window (days)	30 day screening period		7 – 14 days after visit A	21 – 28 days after visit B	7 – 14 days after visit C
Laboratory Assessments	Subject Fasting ^g			X		X
	eGFR ^h	X	X	X	X	X
	Early Morning Void Urine ACR & Urinalysis ⁱ	X	X	X	X	X
	Chemistry & Hematology	X	X	X	X	X
	HbA1c	X				
	HIV-1, HBV, HCV Serology	X				
	Blood Biomarkers			X		X
	CCI					
	Prothrombin Time	X				
	Insulin, Lipid, c-peptide			X		X
	Nt-proBNP			X		X
	cTnI			X		X
	Digoxin ^k				X	
Pregnancy Testing ^l	X		X		X	
FSH Testing ^m	X					
Urine Biomarkers			X		X	

- a. Samples to be collected pre-dose
- b. Subject can have no missed doses of study drug during the 7 consecutive days immediately prior to Visit C and Visit 1
- c. On visits without a scheduled complete physical examination, a symptom-driven physical examination may be performed if necessary
- d. Vital signs include resting blood pressure, pulse, respiratory rate, temperature and weight. Measurements of blood pressure should be taken per institutional guidelines. Subject position should be consistent for each subsequent measure
- e. Subject-reported outcomes should be completed at the start of the study visit and prior to the clinical and laboratory assessments. The subject should read the questionnaires by himself/herself and record the answers by himself/herself. The HRQoL questionnaires to be completed at Enrollment are KDQOL-36, KCCQ, and WPAI-GH

- █ [REDACTED]
- g. Subjects should abstain from all food for at least 8 hours prior to laboratory draw, water is allowed
 - h. eGFR value to be calculated by the Chronic Kidney Disease Epidemiology Creatinine Equation (2009); if eGFR value at Screening does not meet inclusion criteria, subject may repeat 2 additional times during Screening and prior to Enrollment (Visit A). Subject must have eGFR ≥ 15 mL/min/1.73 m² at all central laboratory assessments during the Run-in period prior to Randomization (Visit 1)
 - i. First morning void collection is preferred when possible, but early morning void is accepted. Bring sample to clinic within 1 hour, if not possible, refrigerate and bring to clinic within 12 hours. If UACR value at Screening does not meet inclusion criteria, subject may repeat 2 additional times during Screening and prior to Enrollment (Visit A)
- █ [REDACTED]
- k. For subjects taking digoxin only, digoxin level should be measured at Visit C and Week 4. PI may continue checking after Week 4 as part of digoxin management as needed. Monitor and adjust digoxin dose as necessary based on prescribing information.
 - l. Females of childbearing potential as defined by protocol only (refer to Protocol Appendix 6): Serum pregnancy test at Screening and urine pregnancy test at Visit B, Randomization and every 4 weeks through the 30 Day EOT Follow-up visit.
 - m. FSH testing to determine female subject's postmenopausal state as described in Protocol Appendix 6.

Study Procedures Table – Week 4 to Week 48+

	Period	On Treatment						
	Visit	2	3	4	5	6	7	q12 weeks ¹
	Week	4	8	12	24	36	48	
	Visit Window (days)	±5	±5	±5	±5	±5	±5	
Clinical Assessments	Complete Physical Examination ^a							
	Vital Signs including Weight ^b	X	X	X	X	X	X	X
	Waist Circumference						X	
	12 Lead ECG						X	
	CCI							
	Adverse Events	X	X	X	X	X	X	X
	Concomitant Medications	X	X	X	X	X	X	X
	Study Drug Dispensing	X	X	X	X	X	X	X
	Study Drug Dosing	X	X	X	X	X	X	X
	Study Drug Bottle Return	X	X	X	X	X	X	X

	Period	On Treatment						
	Visit	2	3	4	5	6	7	q12 weeks ^l
	Week	4	8	12	24	36	48	
	Visit Window (days)	±5	±5	±5	±5	±5	±5	
Laboratory Assessments	Subject Fasting ^e						X	
	eGFR ^f	X	X	X	X	X	CCI	X
	Early Morning Void Urine ACR & Urinalysis ^g	X	X	X	X	X	X	X
	Chemistry & Hematology	X	X	X	X	X	X	X
	HbA1c				X		X	X
	Blood Biomarkers	X			X		X	
	Insulin, Lipid, c-peptide						X	
	Nt-proBNP						X	
	cTnI						X	
	Digoxin ^h	X						
	CRP						X	
	Sparse PK ⁱ	X		X	X		X	
	CCI							
	Pregnancy Testing ^k	X	X	X	X	X	X	X
Urine Biomarkers	X			X		X		

- a. On visits without a scheduled complete physical examination, a symptom-driven physical examination may be performed if necessary
 b. Vital signs include resting blood pressure, pulse, respiratory rate, temperature and weight. Measurements of blood pressure should be taken per institutional guidelines. Subject position should be consistent for each subsequent measure

█ [REDACTED]

█ [REDACTED]

- e. Subjects should abstain from all food for at least 8 hours prior to laboratory draw, water is allowed
 f. eGFR value to be calculated by the Chronic Kidney Disease Epidemiology Creatinine Equation (2009)

- g. First morning void collection is preferred when possible, but early morning void is accepted. Bring sample to clinic within 1 hour, if not possible, refrigerate and bring to clinic within 12 hours
- h. For subjects taking digoxin only, digoxin level should be measured at Visit C and Week 4. PI may continue checking after Week 4 as part of digoxin management as needed. Monitor and adjust digoxin dose as necessary based on prescribing information.
- i. Sparse PK samples should only be collected for randomized subjects on study drug

- k. Females of childbearing potential as defined by protocol only (refer to Protocol Appendix 6): Starting after Week 4, every 4 week pregnancy testing may occur at home, where possible, in between in clinic visits or in clinic. At home pregnancy testing kits will be provided. Females of childbearing-potential performing at home pregnancy testing will be contacted every 4 weeks to report the result of the at home pregnancy tests until the 30 Day EOT Follow-up visit.
- l. Repeat every 12 weeks until global study end date.

Study Procedures Table – EOT to 30 Day EOS Safety Follow-up

	Period	EOT ^a	30 Day EOT Follow-up ^b	Limited Assessments ^c	EOS ^d	30 Day EOS Safety Follow-up ^e	
	Visit						
	Week						
	Visit Window (days)						
	Complete Physical Examination ^f	X					
	Vital Signs including Weight ^g	X		X	X		
	Waist Circumference	X					
	12 Lead ECG	X			X		
Clinical Assessments	CCI						
		Adverse Events	X	X	X	X	X
		Concomitant Medications	X	X	X	X	X
		Study Drug Dispensing					
		Study Drug Dosing					
		Study Drug Bottle Return	X				

	Period	EOT ^a	30 Day EOT Follow-up ^b	Limited Assessments ^c	EOS ^d	30 Day EOS Safety Follow-up ^e
	Visit					
	Week					
	Visit Window (days)					
		±7	±7	±7	±7	±7
Laboratory Assessments	Subject Fasting ^j					
	eGFR ^k	X	X	X	X	
	Early Morning Void Urine ACR & Urinalysis ^l	X	X		X	
	Chemistry & Hematology	X	X	X	X	
	HbA1c					
	Blood Biomarkers	X	X		X	
	Blood Glucose					
	Insulin, Lipid, c-peptide					
	Nt-proBNP					
	cTnI					
	CRP					
	Sparse PK ^m	X				
	Pregnancy Testing ⁿ	X	X		X	
Urine Biomarkers	X	X		X		

- EOT assessments should be completed for subjects who meet criterion for study drug discontinuation in Protocol Section 3.4. These assessments should be completed as soon as possible after the decision is made. Every attempt should be made to keep the subject in the study to complete all remaining study visits for outcome assessment. If an ECG or STS was conducted at a previous visit within 24 weeks of the EOT visit, the assessment does not need to be performed at the EOT visit
- Subjects who permanently discontinue study drug must also return to clinic for a 30 Day EOT Follow-up visit 30 days (±7 days) after study drug discontinuation
- Subjects who permanently discontinue study drug are encouraged to continue all study visits per schedule of procedures. However, if a subject requests limited assessments, they may perform these procedures every 12 weeks
- EOS assessments should be completed for subjects who meet criterion for study discontinuation in Protocol Section 3.5. If the subject discontinues study drug and discontinues from the study on the same day, assessments for EOT visit should be completed. The subject will still need to return to clinic 30 days (±7 days) for a 30 Day EOT Follow-up visit and complete the 30 Day EOS Safety Follow-up visit.
- This visit may be conducted in clinic or via telephone

- f. On visits without a scheduled complete physical examination, a symptom-driven physical examination may be performed if necessary
- g. Vital signs include resting blood pressure, pulse, respiratory rate, temperature and weight. Measurements of blood pressure should be taken per institutional guidelines. Subject position should be consistent for each subsequent measure
- h. [REDACTED]
- i. [REDACTED]
- j. Subjects should abstain from all food for at least 8 hours prior to laboratory draw, water is allowed
- k. eGFR value to be calculated by the Chronic Kidney Disease Epidemiology Creatinine Equation (2009)
- l. First morning void collection is preferred when possible, but early morning void is accepted. Bring sample to clinic within 1 hour, if not possible, refrigerate and bring to clinic within 12 hours
- m. Sparse PK testing should be performed for all randomized subjects while on study drug. Sparse PK testing does not need to be collected after study drug is discontinued.
- n. Females of childbearing potential as defined by protocol only (refer to Protocol Appendix 6): Starting after Week 4, every 4 week pregnancy testing may occur at home where possible, in between in clinic visits, or in clinic. At home pregnancy testing kits will be provided. Females of childbearing potential performing at home pregnancy testing will be contacted every 4 weeks to report the result of the at home pregnancy tests until the 30 Day EOT Follow-up visit

Appendix 2. Adjustment of On-Treatment eGFR_{cr} Values

For subjects in the SEL treatment group, the on-treatment eGFR_{cr} values will be adjusted using a regression model. The statistical methods are described below. For subjects in the SEL treatment group whose off-treatment eGFR_{cr} data are not collected, or who experience a decrease in eGFR of $\geq 40\%$ relative to Baseline as a primary clinical endpoint event before treatment discontinuation, their eGFR values after treatment discontinuation will be imputed using a regression model. The statistical methods are described below.

The following linear regression model will be fitted for subjects in the SEL treatment group whose off-treatment eGFR_{cr} values are collected in the study:

$$\delta = \alpha + \beta x + \epsilon$$

Where δ is the change in eGFR_{cr} values after treatment discontinuation defined as the first observed eGFR_{cr} value at least 7 days after treatment discontinuation minus the last observed eGFR_{cr} value before treatment discontinuation; x is the last observed eGFR_{cr} value before treatment discontinuation, α is the intercept, β is the coefficient for x , and ϵ is the residual.

This model will then be used to predict the unobserved eGFR_{cr} change after treatment discontinuation for subjects in the SEL treatment group. Specifically, the x term in the model is the observed eGFR_{cr} value at each visit, and the outcome δ is the predicted eGFR_{cr} change if subject hypothetically discontinues SEL treatment at each visit.

On-treatment eGFR_{cr} values will then be as adjusted by adding δ to the observed eGFR_{cr} values. These adjusted eGFR_{cr} values will be used in the sensitivity analyses for primary and some secondary endpoints, as described in Sections 6.1.3 and 6.2.2.

Appendix 3. Prohibited Medications That May Impact SEL Treatment Efficacy or Decrease SEL Drug Level

Medication	Prohibited Period
Amiodarone	90 days prior to Enrollment through EOS
Bardoxolone	2 weeks prior to Enrollment through EOS
Ranolazine	2 weeks prior to Enrollment through EOS
Dronedarone	2 weeks prior to Enrollment through EOS
Dofetilide	2 weeks prior to Enrollment through EOS
Trimethoprim	2 weeks prior to Enrollment through EOS
Isavuconazole	2 weeks prior to Enrollment through EOS
Pyrimethamine	2 weeks prior to Enrollment through EOS
Cimetidine	2 weeks prior to Enrollment through EOS
Famotidine	2 weeks prior to Enrollment through EOS
Phenobarbital	2 weeks prior to Enrollment through EOT
Phenytoin	2 weeks prior to Enrollment through EOT
Rifampin	2 weeks prior to Enrollment through EOT
St. John's wort	2 weeks prior to Enrollment through EOT

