6.5. Assessments for Subjects who Reach Kidney Failure While on Study Drug

Subjects who reach kidney failure will be instructed to discontinue study drug, complete the EOT and 30 Day (± 7 days) EOT Follow-up visits, which will include an assessment of eGFR and UACR. Following the 30 Day EOT Follow-up visit, subjects who reach kidney failure will continue on study, followed via remote assessments per Section 6.7.3, but no longer followed for the primary efficacy endpoint.

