1.3. Sample Size and Power

With a sample size of 300 subjects (150 per treatment arm), power to detect a difference in $eGFR_{cr}$ decline rate of 3.7 mL/min/1.73 m^2 /year (common SD = 10 mL/min/1.73 m^2 /year) between SEL 18 mg and placebo using a two-sample t-test is 99% at a 1-sided significance level of 0.15. Assuming 15% dropout, with a sample size of 254 (127 per arm), the power is 97%.

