6.1.2. Statistical Hypothesis of the Primary Endpoint

The primary analysis will test the following null hypothesis (H_0) that there is no difference in eGFR_{cr} slope from treatment-specific Baselines between SEL and placebo versus the alternative hypothesis (H_1) that eGFR_{cr} slope in the SEL arm is larger than that in the placebo arm.

Formally,

$$H_0: \beta_{SEL} = \beta_{PBO} \text{ vs. } H_1: \beta_{SEL} > \beta_{PBO}$$

where β_{SEL} and β_{PBO} denote the mean slope from treatment-specific Baselines for SEL and placebo, respectively.

Statistical testing will be conducted at a 1-sided Type 1 error level of 0.15.

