6.1.3. Analysis of the Primary Endpoint

The Primary Analysis Set for efficacy analyses is the Full Analysis Set.

Definition of Baseline

Baseline eGFR_{cr} for the primary analysis is defined as below:

- SEL arm: The average of the measurements at Visit C and Visit 1. This Baseline will also be referred to as post-run-in Baseline.

- Placebo arm: The average of the measurements at Visit A (enrollment) and Visit B. This Baseline will also be referred to as pre-run-in Baseline.

Estimand

The Treatment Policy estimand is defined as follows. This is the primary estimand for the primary endpoint.

- 1) Population: Subjects in the FAS. See definition of the FAS in Section 3.1.3.
- 2) Variable: Primary endpoint (eGFR_{cr} slope from treatment-specific Baselines through Week 84). See Section 6.1.1 for detailed definition of the primary endpoint.
- 3) Intercurrent events: Intercurrent events for this study include study treatment discontinuation and/or starting a concomitant medication (e.g. SGLT-2 inhibitors).

The occurrence of an intercurrent event is irrelevant. All observed values will be used regardless of occurrence of an intercurrent event.

- All observed values will be used regardless of occurrence of an intercurrent event (i.e, All available data defined above)
 - If a subject is lost to follow up, treat data as missing from the point of loss to follow-up onward
- 4) Population-level summary: eGFR_{cr} slope from treatment-specific Baselines through Week 84 in each treatment arm, and difference in eGFR_{cr} slope from treatment-specific Baselines through Week 84 between SEL and placebo treatment arms.

Main Estimator

A random slope model will be used to evaluate SEL treatment effect on eGFR_{cr} slope from treatment-specific Baselines through Week 84. The random slope model will have eGFR_{cr} change from treatment-specific Baselines at Weeks 4, 8, 12, 24, 36, 48, 60, 72 and 84 as outcome, and will include terms for eGFR_{cr} at treatment-specific Baselines as a continuous variable, pre-run-in Baseline UACR category (< 1500 mg/g vs. ≥ 1500 mg/g), concomitant use of SGLT-2 inhibitors at Randomization, treatment group, week, and treatment-by-week interaction. Within-subject variance covariance will be modeled as unstructured. If model convergence problems arise, other variance-covariance structures, such as Heterogeneous Toeplitz, will be considered and documented.

Sensitivity analyses of the eGFR_{cr} slope endpoint will include the following:

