- Sensitivity analysis of eGFR_{cr} slope excluding off-treatment eGFR_{cr} values from the SEL treatment group.

- Sensitivity analysis of eGFR_{cr} slope excluding eGFR_{cr} values collected after the initiation of dialysis or kidney transplantation.
- Sensitivity analysis to evaluate the impact of attenuation of the acute effect. For subjects in the SEL group, the on-treatment eGFR_{cr} values will be adjusted using a regression model as described in [Appendix 2](#), which takes into account attenuation of the acute treatment effect that may be due to the theoretical concern for loss of kidney function over time. For subjects in the placebo group, the observed eGFR_{cr} values will be used. The analysis of eGFR_{cr} slope will be performed using the same model as described in the primary analysis, except that pre-run-in Baseline eGFR_{cr} will be used for both SEL and placebo arms.
- Sensitivity analysis of eGFR_{cr} slope in subjects who completed study treatment.
- Sensitivity analysis of eGFR_{cr} slope excluding subjects with randomization stratification mismatch between IXRS and Clinical Database.
- Sensitivity analysis of eGFR_{cr} slope excluding subjects who took prohibited medications that may affect SEL efficacy or decrease SEL drug level in the prohibited period as detailed in [Appendix 3](#).
- Sensitivity analysis of eGFR_{cr} slope from pre-run-in Baseline for both SEL and placebo arms.
- Sensitivity analysis of eGFR_{cr} slope from treatment-specific Baselines through Week 48.
- Sensitivity analysis of eGFR_{cr} slope from treatment-specific Baselines through Week 60.
- Sensitivity analysis of eGFR_{cr} slope from treatment-specific Baselines through Week 72.
- Sensitivity analysis of eGFR_{cr} slope from treatment-specific Baselines through Week 96.

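### SAP Appendix 2 calls for post-discontinuation eGFR to be imputed in two SEL subgroups only, in one of them over measured values, and conflicts with the sections that use it

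*SAP*

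**What the plan says.** The opening paragraph of SAP Appendix 2 first says that SEL on-treatment eGFRcr will be adjusted by regression, as the appendix title suggests. Its third sentence adds a separate rule for SEL subjects after they stop drug. It applies if off-treatment eGFRcr was not collected, or if the subject had a fall of at least 40% "relative to Baseline as a primary clinical endpoint event before treatment discontinuation, their eGFR values after treatment discontinuation will be imputed".

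The only model given is δ = α + βx. Here x is the last value before stopping, and δ is the change from it to the first value at least 7 days after stopping. It is fitted to SEL subjects with off-treatment data. The application spelled out takes x as the observed eGFR at each visit and adds δ to on-treatment values. The appendix then sends these adjusted values to the sensitivity analyses of Sections 6.1.3 and 6.2.2.

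The calling sections are narrower than the third sentence. Section 6.1.3 has a sensitivity analysis in which SEL on-treatment values are adjusted by a model "which takes into account attenuation of the acute treatment effect that may be due to the theoretical concern for loss of kidney function over time", placebo values are used as observed, and both arms use the pre-run-in baseline. Section 6.2.2.2 does the same for kidney events. Neither mentions imputing values after discontinuation. For the primary estimand, Section 6.1.3 says "All observed values will be used regardless of occurrence of an intercurrent event", and data after loss to follow-up are treated as missing.

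**The concern.** The primary analysis starts each arm from a different baseline. Among the slope checks in Section 6.1.3, the attenuation analysis is the only one that moves SEL on-treatment values to an off-drug scale and compares them with placebo from a common baseline. It should therefore treat the arms alike in every other respect.

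The third sentence does not. It fills in or replaces post-stop values in SEL and has no placebo counterpart. One of its triggers is the outcome itself. It also calls the 40% fall a primary clinical endpoint event, which this trial does not have: the primary endpoint is a slope, and the 40% fall is a component of a secondary endpoint (SAP 6.2.1). It does not say which baseline defines the fall, although SAP 3.8.3 defines three.

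At stake is a check that could lean towards SEL even if the drug had no effect on progression.

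**Working it through.** **1. Who is covered.** Let A be SEL stoppers with no off-treatment data, and B be SEL stoppers with a fall of at least 40% before stopping. The rule covers A or B. Anyone in both is already covered by A, so B adds only subjects whose off-drug values were measured. Nothing removes them from the model fit either. Their first off-drug value would help to estimate α and β and would then be replaced by the prediction.

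**2. What value they receive.** The SAP leaves three possibilities.
- *Later uncollected visits are filled.* No eGFR was observed at those visits, so the only available x is the last on-drug value, x_L. The imputed value is x_L + α + βx_L. Time does not appear, so every later visit gets the same number.
- *One value per stopper is filled.* There is then no flat stretch.
- *x is the measured off-drug value (group B).* An off-drug correction is added to a value already off drug. The dip was reversible in the Phase 1b study (Protocol 1.2.3.1), so δ is expected to be positive and SEL would be raised again.

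**3. On-treatment adjustment is a separate matter.** There the adjusted value is α + (1+β) × observed, so a slope is multiplied by (1+β). A slope of −4.97 becomes −4.47 at β = −0.1, stays −4.97 at β = 0, and becomes −5.52 at β = +0.11. Nothing is held flat by this step.

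**4. The plan's own figure.** The SAP gives no figure for Appendix 2, so its power statement is used to check the test formula.
- Inputs (SAP 1.3 and 6.1.2): "With a sample size of 300 subjects (150 per treatment arm), power to detect a difference in" eGFRcr "decline rate of 3.7 mL/min/1.73 m"² per year, SD 10; "Statistical testing will be conducted at a 1-sided Type 1 error level of 0.15"; "Assuming 15% dropout, with a sample size of 254 (127 per arm), the power is 97"%.
- 150 per arm: SE = 10 × √(2/150) = 1.155; Φ(3.7/1.155 − 1.036) = 98.5% (stated 99%).
- 127 per arm: SE = 10 × √(2/127) = 1.255; Φ(3.7/1.255 − 1.036) = 97.2% (stated 97%).

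**5. Size if values are carried flat to Week 84.** Inputs are a decline of −4.97 per year in both arms (earlier Phase 2 placebo group, Protocol Table 1-2), the visits in SAP 6.1.3 plus Week 0, and a least-squares slope per subject. The share f of SEL subjects imputed is an assumption. Its top value, 28.9%, is the share who stopped SEL 18 mg in that study (Protocol 1.2.3.2.2), which is an upper bound because not every stopper would be imputed.

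For a Week 36 stop, in weeks: Sxx = 20,240 − 348²/10 = 8,129.6. With times capped at 36, Sxy = 11,600 − 348 × 228/10 = 3,665.6. The ratio is 0.451, so the fitted slope is −4.97 × 0.451 = −2.24, a shift of +2.73. Arm bias is f × shift, and one-sided error is Φ(bias/1.155 − 1.036).

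| Stop week | Shift per imputed subject | f = 5%: bias (error) | f = 15% | f = 28.9% |
|---|---|---|---|---|
| 24 | +3.65 | 0.18 (0.19) | 0.55 (0.29) | 1.06 (0.45) |
| 36 | +2.73 | 0.14 (0.18) | 0.41 (0.25) | 0.79 (0.36) |
| 48 | +1.81 | 0.09 (0.17) | 0.27 (0.21) | 0.52 (0.28) |
| 60 | +0.99 | 0.05 (0.16) | 0.15 (0.18) | 0.29 (0.22) |

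The nominal error is 0.15, and these errors belong to the sensitivity test only.

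**6. Simulation with no true effect on progression.** There were 240 trials per setting with 150 per arm. All of the following are assumed: eGFR mean 36, slope −5 (SD 5) per year, reading CV 8%, a persistent 8% dip on SEL, 25% stopping at random by Week 48 plus a stop at confirmed eGFR below 15, and the off-drug adjustment taken as known.
- No imputation: slope difference −0.05 to −0.01; rejection 13–14%.
- Later visits imputed, with 5%, 15% and 30% of SEL stoppers lacking off-drug data: +0.10, +0.18 and +0.37; rejection about 17%, 23% and 31%.
- Overwriting measured values after a 40% fall, alone: about +0.05.
- One imputed value per stopper: about +0.07.
- Kidney events: a change of under one SEL event.

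The Monte Carlo SE near 15% is √(0.15 × 0.85/240) = 2.3 points, so the step from 13–14% to 17% is not clear on its own.

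**The case against.** The strongest defence is that the sentence is orphan text. The closing lines of Appendix 2 send only adjusted on-treatment values to the sensitivity analyses, the model is said to predict a change that was unobserved, and the calling sections ask for nothing more. A careful programmer might impute nothing. That stands as a reason not to claim a demonstrated bias. It does not rescue the sentence, which is mandatory in form and contradicts its surroundings. The general rule in SAP 3.6.1 against imputation gives way where a method is specified, and Appendix 2 specifies one.

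It can also be said that, since no primary clinical endpoint event exists here, the second condition captures nobody. That reading is possible. It leaves the first condition in force and shows that the wording does not fit this trial.

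The evidence for measured off-drug data needs care. Protocol 6.5 schedules "EOT Follow-up visits, which will include an assessment of eGFR and UACR", but for kidney failure rather than a 40% fall, and remote follow-up afterwards lists no eGFR (Protocol 6.7.3). A 40% fall is not a stopping reason in Protocol 3.4. The better support is Protocol 6.7.1 and 6.7.2, under which other stoppers continue visits with eGFR.

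On importance, this is one of 11 sensitivity analyses of the primary endpoint. The slope from pre-run-in baseline in both arms and the eGFRcys slope do not use Appendix 2. The overwrite alone is about 1% of the design difference (0.05/3.7). With the fitted rather than a known adjustment, simulated rejection was already 27% before imputation and 37% after it (15% uncollected), so much of that excess has another source. All of this stands and limits the weight of the point.

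**Conclusion.** The sentence is wrong as written and should go, but the point is modest. It sets a SEL-only imputation for two named subgroups, one triggered by the outcome, with no time term, no rule on which visits are filled and no placebo counterpart. It conflicts with the appendix title and with Sections 6.1.3 and 6.2.2.2.

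Any bias is expected to favour SEL. It is about 0.05 mL/min/1.73 m²/year for the overwrite alone or when few, late stoppers are imputed. It reaches several tenths, and about 1 at the extreme, if values are carried flat to Week 84. These figures rest on assumed shares, stop times and decline rates. The actual size cannot be derived from the documents.

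A reader might infer three stronger things that the documents do not support:
- *SEL stoppers are held flat while placebo stoppers keep declining.* The SAP states no carry-forward rule. SEL stoppers with off-drug data and no prior 40% fall keep their values. Placebo decline is seen only where it was measured.
- *The primary result is biased by this rule.* The primary analysis uses all observed values in both arms and does not call Appendix 2.
- *A long measured decline after kidney failure is discarded.* Scheduled eGFR for those subjects ends at the 30 Day EOT Follow-up visit.

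**What to change.** In SAP Appendix 2, delete the third sentence of the opening paragraph (the one that imputes SEL values after discontinuation) and the repeated pointer to the methods that follows it. State instead that:
- only SEL on-treatment values are adjusted;
- every measured off-treatment value is used unchanged in both arms, including after a fall of at least 40%;
- uncollected post-stop values stay missing in both arms, so that the mixed model treats the arms alike.

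If the sponsor prefers to keep an imputation, the SAP should name the visits filled, protect measured values, include time since stopping, identify the baseline, and apply a matching rule to placebo.

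Deletion changes SAP wording only. It removes a programming step and needs no new data.
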